Overall survival at Day 100 (days) is defined as survival from the day of TA-TMA diagnosis and will be analyzed using Kaplan-Meier model. Kaplan-Meier survival estimate at Day 100 and its 95% CI will be presented. Counts and proportions of patients with events and censored will be presented, together with estimates of median and quartiles obtained from the model. Kaplan-Meier curves will also be presented. Death for any cause will be considered an event, with the date of death defining the event date. Patients alive on the date of last contact will be censored on this date. Pegcetacoplan-withdrawn patients for which survival at Day 100 is unknown will be censored at the date of last contact. If the event/censored date is more than 100 days from the start date, the patient will be considered censored at 100 days.

8.8.2.5 OVERALL SURVIVAL AT WEEK 24

The start date for overall survival at Week 24 from treatment start will be defined as the date of first exposure

Page 26 of 39

to the study drug. Death for any cause will be considered an event, with the date of death defining the event date. Patients alive at the end of the study visit will be considered censored at the date of the visit.

Overall survival at Week 24 (weeks) will be analyzed in the same way as Overall survival at Day 100 (see Section §8.8.2.4 for details).

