8.8.2.6 TIME TO CLINICAL RESPONSE

Time to clinical response (weeks) will be defined as the date of first exposure to the study drug to the first occurrence of clinical response (derived as in Appendix I [Section 13.1]). Time to clinical response (weeks) will be evaluated for:

- Patients achieving clinical response (without a preceding ICE) at any time during the study. Note the patient in this case will be considered as a responder even if not any longer in clinical response at week 24 or not (sustained response not required)
- Patients achieving clinical response at Week 24 without meeting an ICE (response must be sustained until Week 24)

In sustained response, if the patient has a missing evaluation at Week 24, this patient will not be considered as a responder and will be censored on the day after the last previous assessment in which the response could be evaluated. Patients without clinical response at any visit up to Week 24 will be censored on the day after the last previous assessment in which response could be evaluated. Patients with no clinical response evaluation visits will be excluded from the analysis.

In case clinical response is lost, and redetected, the date of clinical response will be defined as the date when the most recent clinical response was detected. For sustained response, this date will be the event date if the patient is in clinical response at week 24.

The time to clinical response (weeks) will be analyzed in the same way as Overall survival at Day 100 (see Section §8.8.2.4 for details). Nevertheless, Kaplan-Meier curves will be presented as increasing curves as the event here is positive.

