8.8.2.7 TIME TO TMA RESPONSE

Time to TMA response (weeks) will be defined as the date of first exposure to the study drug to first occurrence of TMA response (derived as in Appendix II [Section 13.2]). Time to TMA response (weeks) will be evaluated for:

- Patients achieving TMA response (without a preceding ICE) at any time during the study. Note the
 patient in this case will be considered as a responder even if not any longer in TMA response at week
 24 or not (sustained response not required)
- Patients achieving TMA response at Week 24 without meeting an ICE (response must be sustained until Week 24)

The time to TMA response (weeks) will be analyzed in the same way as Time to Clinical Response (see Section §8.8.2.6 for details).

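### Week 24 survival and time to response borrow from the Day-100 survival section without excluding its 100-day cut-off, which conflicts with their own rules

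*SAP*

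**What the plan says.** SAP 8.8.2.4 defines Day-100 survival from TA-TMA diagnosis, sets out the Kaplan-Meier outputs, censors patients at last contact, and closes with the truncation rule: "If the event/censored date is more than 100 days from the start date, the patient will be considered censored at 100 days". The rule is tied to a start date in general, not to the date of diagnosis.

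Three later sections depend on it:

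- **SAP 8.8.2.5, Week 24 survival.** It sets its own start (first exposure), counts death from any cause as an event, and adds: "Patients alive at the end of the study visit will be considered censored at the date of the visit". It then says: "Overall survival at Week 24 (weeks) will be analyzed in the same way as Overall survival at Day 100", pointing to 8.8.2.4 for details.
- **SAP 8.8.2.6, time to clinical response.** One version covers "Patients achieving clinical response (without a preceding ICE) at any time during the study"; the other requires response sustained to Week 24. On censoring: "Patients without clinical response at any visit up to Week 24 will be censored on the day after the last previous assessment" at which response could be evaluated. It then says: "The time to clinical response (weeks) will be analyzed in the same way as Overall survival at Day 100", again pointing to 8.8.2.4, with one qualification to that reference: "Nevertheless, Kaplan-Meier curves will be presented as increasing curves as the event here is positive".
- **SAP 8.8.2.7, time to TMA response.** "The time to TMA response (weeks) will be analyzed in the same way as Time to Clinical Response", so it reaches 8.8.2.4 at one remove.

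Protocol 8.3.4.2 also evaluates Week 24 survival like Day-100 survival, but it contains no 100-day truncation. The question arises only in the SAP.

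**The concern.** A 100-day cut-off is right for an endpoint defined at Day 100. It is wrong for one defined at Week 24, and for a time to response observed over 24 weeks. Because the cross-references do not exclude it, a programmer following them in full would apply it to all three later analyses. A death on Day 130 would be coded as censored, although 8.8.2.5 counts any death as an event. A first response at Week 16, 20 or 24 would be coded as censored, although 8.8.2.6 counts a response at any time in the study.

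At stake are three named secondary endpoints, one of them survival. Protocol 8.3.8 also carries the same type of methodology into the BATAP subgroup analyses of survival. Duration of response (SAP 8.8.2.8 and 8.8.2.9) does not refer to 8.8.2.4 and is not affected.

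**Working it through.** **Plan's own figure.** The plan gives no figure that depends on this rule. Its one computed design figure, a 72% probability of at least 8 responders among 12 at a true rate of 70%, reproduces (exact binomial tail 0.7237) and is untouched by the point.

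**1. Local text against the borrowed rule**

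| Element | Local text (8.8.2.5 to 8.8.2.7) | Borrowed from 8.8.2.4 if literal |
|---|---|---|
| Death after day 100 (8.8.2.5) | Event | Censored at day 100 |
| Alive at end of study (8.8.2.5) | Censored at that visit, target Day 169 | Censored at day 100 |
| First response after day 100 (8.8.2.6, 8.8.2.7) | Event | Censored at day 100 |
| No response to Week 24 (8.8.2.6, 8.8.2.7) | Censored the day after the last evaluable assessment | Censored at day 100 if that is later than day 100 |
| Withdrawn or lost before the end-of-study visit (8.8.2.5) | Not stated | Censored at last contact, then the 100-day rule |
| Time point of the estimate (8.8.2.5) | Not stated | Day 100 |

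The first four rows are conflicts. The last two are gaps that the analyst can fill only from 8.8.2.4, where the 100-day sentence directly follows the last-contact rule.

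**2. Horizon lost.** Week 24 is study Day 169 (SAP Table 1). Day 1 is the day of first dose, so this is 169 − 1 = 168 days from first dose. Cut at 100 days: 168 − 100 = 68 days, and 68/168 = 40.5%. The curve would stop at 100/7 = 14.3 weeks.

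**3. Evaluations lost.** The post-baseline response evaluations in Protocol Table 1 fall on Days 8, 15, 22, 29, 43, 57, 71, 85, 99, 113, 141 and 169. Days 113, 141 and 169 are 112, 140 and 168 days from first dose, all beyond 100. Patients treated for 12 weeks skip Day 99, so 3 of 11 evaluations can no longer yield an event; for 16-week patients it is 3 of 12. In the sustained version, a response lost and regained takes the later date, so a response regained after day 100 would be lost too.

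**4. Illustration with 12 hypothetical patients.** Deaths at days 40, 80, 120 and 150; eight alive at day 168.

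- Followed to 168 days: 4 deaths, Week 24 survival 8/12 = 66.7%.
- Cut at 100 days: 2 deaths, the curve ends at day 100 at 10/12 = 83.3%, and there is no estimate at Week 24.

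For response, take first responses at days 28, 56, 56, 84, 84, 112, 112 and 140, with four non-responders. The full horizon gives 8 events (66.7%); the 100-day cut gives 5 (5/12 = 41.7%).

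**5. Range under an assumption.** The documents give no Week 24 mortality. Assume a constant hazard, so that S(100) = S(168)^(100/168). Expected deaths recoded as censored are 12 × [S(100) − S(168)].

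| Assumed S(168) | S(100), last plotted value | Difference (points) | Deaths recoded, of 12 |
|---|---|---|---|
| 70% | 81% | 11 | 1.3 |
| 60% | 74% | 14 | 1.7 |
| 50% | 66% | 16 | 1.9 |
| 40% | 58% | 18 | 2.2 |

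Over Week 24 mortality of 20% to 75%, the recoded deaths run from 0.9 to 2.3. If deaths cluster early, fewer fall after day 100 and the effect is smaller.

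**The case against.** The strongest reply is that the cross-reference cannot be meant in full. Taken that way, 8.8.2.6 would also import the diagnosis date as its start and death as its event, which is absurd. Sections 8.8.2.5 to 8.8.2.7 set their own starts and events, and 8.8.2.5 and 8.8.2.6 their own censoring rules, all running to the end-of-study visit or Week 24. What they borrow is then the Kaplan-Meier estimate, interval, counts, quartiles and curves, and a specific local rule should prevail over a general pointer. Protocol 8.3.4.2 has no truncation, and SAP section 10 lists none among its deviations from the protocol. The study is a descriptive pilot. Deaths are summarised and listed, response is summarised at every visit, and a Week 24 curve stopping at 14.3 weeks would be noticed.

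Most of this stands. Borrowing the method only is the likely intent. A reader might infer that the only departure 8.8.2.6 makes from 8.8.2.4 is the direction of the curve; its own event and censoring rules show otherwise. A reader might also infer that the SAP settles the removal of late deaths and responses; it does not, because its local text says the opposite.

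What does not stand is that the local text resolves the matter. The SAP has no rule of precedence. Section 8.8.2.5 says nothing about patients who leave before the end-of-study visit, so the analyst must go back to 8.8.2.4 for censoring, and nothing there says to take one censoring sentence and leave the next. Even on the benign reading, no Kaplan-Meier estimate at Week 24 is specified.

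**Conclusion.** The point holds as an internal conflict that gives a wrong result if followed literally. It does not show that late events will in fact be removed. Under literal programming, 68 of 168 days (40.5%) are cut, deaths after day 100 become censored, Week 24 survival cannot be estimated, and three scheduled evaluations can no longer produce a first response. These consequences follow from the schedule and the text alone.

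The size of any bias does not. It is tempting to say that Week 24 survival would be overstated by 11 to 18 points. That range rests on assumed survival of 70% to 40% and a constant hazard, neither of which is in the documents. The 81% to 58% are also day-100 values at the end of a truncated curve, not Week 24 estimates; they would mislead only if read as such.

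The analyses are descriptive and the endpoints secondary, so this does not threaten the study. It should still be corrected, because survival is affected and, with 12 patients, one death is about 8 points (1/12).

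**What to change.** Amend four SAP sections:

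- **8.8.2.4:** state that truncation at 100 days applies only to Day-100 survival.
- **8.8.2.5:** state that the Kaplan-Meier estimate and its 95% CI are given at Week 24, 168 days from first dose; that patients without an end-of-study visit are censored at last contact; and that any administrative truncation is at Week 24. Word this to fit the existing rule that censors living patients at the end-of-study visit. That visit has a window of ±3 days around Day 169 (Days 166 to 172, or 165 to 171 days from first dose), so some survivors may be censored shortly before day 168.
- **8.8.2.6 and 8.8.2.7:** state that no 100-day truncation applies.

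The cost is a few sentences. It needs no new data and no change to the design or sample size. The Protocol needs no change on this point.

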8.8.2.6 TIME TO CLINICAL RESPONSE

Time to clinical response (weeks) will be defined as the date of first exposure to the study drug to the first occurrence of clinical response (derived as in Appendix I [Section 13.1]). Time to clinical response (weeks) will be evaluated for:

- Patients achieving clinical response (without a preceding ICE) at any time during the study. Note the patient in this case will be considered as a responder even if not any longer in clinical response at week 24 or not (sustained response not required)
- Patients achieving clinical response at Week 24 without meeting an ICE (response must be sustained until Week 24)

In sustained response, if the patient has a missing evaluation at Week 24, this patient will not be considered as a responder and will be censored on the day after the last previous assessment in which the response could be evaluated. Patients without clinical response at any visit up to Week 24 will be censored on the day after the last previous assessment in which response could be evaluated. Patients with no clinical response evaluation visits will be excluded from the analysis.

In case clinical response is lost, and redetected, the date of clinical response will be defined as the date when the most recent clinical response was detected. For sustained response, this date will be the event date if the patient is in clinical response at week 24.

The time to clinical response (weeks) will be analyzed in the same way as Overall survival at Day 100 (see Section §8.8.2.4 for details). Nevertheless, Kaplan-Meier curves will be presented as increasing curves as the event here is positive.

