#### 8.3.4.2 Analysis of secondary efficacy endpoints

The secondary efficacy endpoints are described in Section 5.2.1.

A secondary endpoint is clinical response at 24 weeks. A composite estimand is used where patients meeting intercurrent events are considered as failures. The intercurrent events of interests are use of prohibited medication or study withdrawal before Week 24. Patients meeting these intercurrent events will be considered as failures/nonresponders.

A 2-sided 95 % confidence interval for the proportion will be calculated using the Clopper-Pearson method.

Clinical response at Week 12 as well as TMA response at Week 12 and Week 24 will be evaluated the same way as clinical response at Week 24.

Another secondary endpoint is overall survival at Day 100 from diagnosis of TA-TMA. Pegcetacoplan withdrawn patients for which survival at Day 100 is unknown will be censored at the date of last contact. Kaplan-Meier curve estimates of survival at Day 100 and survival curves will be estimated.

Overall survival at Week 24 from study Day 1 will be evaluated the same way as overall survival at Day 100 from diagnosis of TA-TMA.

Time to clinical response will be defined as the time from study Day 1 to first occurrence of clinical response and will be evaluated for:

- Patients achieving clinical response (without a preceding ICE) at any time during the study.
- Patients achieving clinical response at Week 24 without meeting an ICE.

Time to clinical response will be analyzed using Kaplan-Meier methodology. Kaplan-Meier curves and estimates will be presented.

Time to TMA response will be evaluated in the same way as time to clinical response.

Duration of clinical response is defined as the time from the first observed clinical response until the response criteria is no longer fulfilled or until end of study. Duration of response will be defined for patients with clinical response without meeting an ICE. Duration of clinical response will be analyzed using Kaplan-Meier methodology. Kaplan-Meier curves will also be presented.

Duration of TMA response will be evaluated the same way as duration of clinical response.

TA-TMA relapse at Week 24 will be defined for patients reaching clinical response at some point of the study. Counts and proportions of patients with and without relapse at Week 24 will be summarized.

The analysis of the secondary endpoints will be performed on the ITT set.

Confidential Page 64 of 89

Pegcetacoplan/TA TMA

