8.8.2 Analysis of Secondary Efficacy Endpoints

8.8.2.1 BIOMARKERS OF COMPLEMENT ACTIVATION

Biomarkers of complement activation: sC5b-9, C3a, C3, Bb, C4a, functional assays for classical and alternative complement pathways will be summarized by visit. Absolute values, changes from baseline, and percent changes from baseline will be summarized. The summaries will be done on PD set. Plots over time for biomarker results for individual patients will be prepared.

8.8.2.2 CLINICAL RESPONSE AT WEEK 24

Clinical response at Week 24 will be summarized. Counts and proportions of clinical response will be reported. 95% Clopper-Pearson confidence interval (CI) for proportion of responders will also be presented. Additionally, clinical response results will be summarized for all visits similar to what was done for Week 24. Patients meeting intercurrent events (ICE), including use of prohibited medication (Plasma exchange – identified by manual review, Defibrotide – ATC code B01AX and manual review, , complement inhibitors – ATC code L04AJ) or withdraw from the study before Week 24 are considered as failures/non-responders at all the visits occurring after the medication/withdrawal. The number and percentage of patients who had an ICE and by ICE category will be presented as well. Medical review of the programmatically generated list of prohibited medications will be performed prior to interim analysis and final database lock.

In addition, investigator assessed response will be summarized per visit. Counts and proportions of response categories (clinical response, partial response, and clinical worsening) will be reported.

8.8.2.3 TMA RESPONSE AT WEEK 24

TMA response at Week 24 is defined as improvement in laboratory markers as follows:

- LDH < 1.5 x ULN **and**
- Platelet count ≥ 50*10^9/L (50 000/mm³) without transfusion support during the prior 7 days and
- ≥ 50 % reduction from baseline in rUPCR

TMA response will be analyzed in the same way as Clinical Response at Week 24 (see Section §8.8.2.2 for details).

8.8.2.4 OVERALL SURVIVAL AT DAY 100

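### Time to clinical and TMA response: censoring pre-response deaths and withdrawals and dropping never-evaluated ITT patients can overstate how many respond and how fast

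*SAP*

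**What the plan says.** Protocol 8.3.4.2 defines time to clinical response as "time from study Day 1 to first occurrence of clinical response", names Kaplan-Meier as the method, gives no censoring rule, and places the secondary endpoints on the ITT set. For response at a visit it uses a composite strategy in which study withdrawal or prohibited medication counts as failure. SAP 8.8.2.2 repeats this: such patients "are considered as failures/non-responders at all the visits occurring after the medication/withdrawal".

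SAP 8.8.2.6 supplies the rules for time to response:

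- Non-responders: "Patients without clinical response at any visit up to Week 24 will be censored on the day after the last previous assessment" that allowed response to be evaluated.
- Never evaluated: "Patients with no clinical response evaluation visits will be excluded from the analysis".
- Sustained analysis: "if the patient has a missing evaluation at Week 24, this patient will not be considered as a responder and will be censored".
- Response lost and regained: "the date of clinical response will be defined as the date when the most recent clinical response was detected".

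The method is borrowed from overall survival at Day 100 (SAP 8.8.2.4), including median and quartiles, but plotted upwards. That section also promises: "Counts and proportions of patients with events and censored will be presented". For TMA response, SAP 8.8.2.7 says: "The time to TMA response (weeks) will be analyzed in the same way as Time to Clinical Response".

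**The concern.** The non-responder rule is a catch-all. It does not name death or study withdrawal, but it has no exception for them, and the section it borrows from treats death only as the event of interest. A patient who dies without responding is therefore censored.

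One minus Kaplan-Meier assumes that censored patients would go on to respond at the rate of those still followed. That is impossible after death, which is a competing event. For patients who withdraw alive the charge is narrower: the curve is too high relative to the composite strategy the plan uses for response at a visit. The plan did consider death nearby, since SAP 8.8.2.8 makes it an event for duration of response.

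The sustained analysis has the same gap: a responder who dies before Week 24 has no Week 24 evaluation and is censored. Excluding never-evaluated patients departs from the protocol's ITT rule, and SAP section 10 does not list it among its two departures.

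Prohibited medication is not part of the problem. Responses count only without a preceding intercurrent event, and under Protocol 6.3.3.1 patients who stop treatment should still attend all follow-up visits, so they can be evaluated to Week 24.

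At stake are the curve, its time-point estimates and its median, which readers take as how many patients respond and how quickly.

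**Working it through.** **Inputs.** N = 12 (SAP section 5). Evaluation visits at Weeks 1, 2, 3, 4, 6, 8, 10, 12, 14, 16, 20 and 24 (Protocol Table 1). Censoring falls just after the last evaluation (SAP 8.8.2.6). The plan gives no figure for time to response to reproduce, and no distribution of response, death or withdrawal times, so the data sets below are assumptions.

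**Formulas.** The SAP curve is 1 − ∏(1 − d/n), with d responses among n at risk at each visit. When every patient responds, has a competing event, or is followed to the end, the Aalen-Johansen cumulative incidence equals responders/12.

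**(a) Six responders (Weeks 4, 6, 8, 10, 12, 16), three losses without response, three non-responders seen to Week 24.** True share 6/12 = 50.0%.

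- Losses last seen at Weeks 1, 2, 3: nine at risk at Week 4, so 1 − 3/9 = 66.7%. The curve passes 50% at Week 12; counting all 12 patients, 50% is reached at Week 16.
- Last seen at Weeks 3, 6, 10: 1 − (10/11)(9/10)(7/8)(6/7)(4/5)(3/4) = 63.2%.
- Last seen at Weeks 16, 20, 20: 50.0%, no bias.

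With random timings (15,000 draws, losses uniform over visits to Week 20):

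| Responses spread over | Losses | Mean 1 − KM | 5th–95th percentile |
|---|---|---|---|
| all visits to Week 24 | 3 | 60.4% | 53.3–65.6% |
| visits to Week 12 | 3 | 56.2% | 50.0–63.9% |
| all visits to Week 24 | 1 | 52.8% | maximum 54.5% |
| visits to Week 12 | 1 | 51.8% | maximum 54.5% |

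**(b) One loss only.** The maximum in the last two rows is 6/11 = 54.5%.

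**(c) One never-evaluated patient excluded.** 6/11 = 54.5% against 6/12 = 50.0%. Evaluations start at Week 1, so this group is likely to be 0 or 1 patient.

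**(d) Median.** Five responders (Weeks 4, 6, 8, 10, 12), losses last seen at Weeks 1, 2, 3, four seen to Week 24. Nine are at risk from Week 4; the response-free share is 5/9 after Week 10 and 4/9 after Week 12. The curve ends at 55.6% with median Week 12. On all 12 patients it is 5/12 = 41.7% and the median is not reached.

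**(e) Sustained analysis.** Four sustained responders (Weeks 4, 6, 8, 12), three deaths last evaluated at Weeks 3, 10, 16 (two of them after a response), five seen to Week 24: 1 − (10/11)(9/10)(8/9)(6/7) = 37.7% against 4/12 = 33.3%. The range is 33.3% (all lost after Week 12) to 4/9 = 44.4% (all lost by Week 3).

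**(f) Where to hold non-responders, if that route is chosen.** Five earlier responders; one responder and three non-responders seen on Day 171; three patients held. Holding to Day 169 leaves four at risk on Day 171: 1 − (7/12)(3/4) = 56.25%. Holding to Day 183, the end of the Week 24 window in SAP Table 1, leaves seven: 1 − (7/12)(6/7) = 50.0% = 6/12.

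**Date of response.** Protocol 8.3.4.2 and the opening of SAP 8.8.2.6 use the first occurrence. The later SAP sentence substitutes the latest detection after a loss, without restricting this to the sustained analysis. Two programmers could derive different any-time dates.

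**The case against.** The best defence is that Kaplan-Meier is the protocol's own choice, nothing is tested, and the number who respond is answered elsewhere: response proportions with Clopper-Pearson intervals at every visit, event and censoring counts beside the curve, and deaths by cause. The bias may be small. One loss adds 2 to 3 points on average. With responses by Week 6, one loss adds about 1.0 point and three add about 3.4. The exact interval for 6/12 runs from 21.1% to 78.9%. The largest figures need all losses before the first response. Censoring a living patient at last evaluation is ordinary practice, and excluding a never-evaluated patient gives the same curve as censoring at Day 1. SAP 8.8 permits stated exceptions to ITT. The latest-detection rule moves dates later, which can partly offset the speed bias.

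Much of this stands, and it limits the point to a descriptive output. Protocol 6.3.3.2 expects withdrawal to be uncommon, and the 60% to 75% mortality in Protocol 4.1 has no time horizon. The estimate that 9 of 12 complete four weeks concerns treatment, not evaluation, so it cannot forecast losses. But none of this makes a patient who died able to respond, and published counts do not correct a published median. The SAP's general allowance for exceptions does not reconcile the exclusion with the protocol.

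**Conclusion.** The concern holds. As written, SAP 8.8.2.6 and 8.8.2.7 give an estimate that is too high whenever a patient dies before responding and others respond later. For live withdrawals the same is true relative to the plan's composite strategy.

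The excess ranges from none to about 17 points with three losses and six responders, and is at most 4.5 points with one. A median can appear when fewer than half the patients responded. These sizes depend wholly on the assumed number and timing of losses; there is no bias if nobody is lost before the last response. The change should be made, though no formal conclusion of the trial depends on it. The conflict over the response date is a separate wording fault.

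**What to change.** 1. Keep every ITT patient in the analysis, count never-evaluated patients as non-responders, and delete the exclusion sentence.
2. Report the Aalen-Johansen cumulative incidence of response, with pre-response death and (under the composite strategy) pre-response study withdrawal as competing events. In the sustained analysis, use any death or withdrawal before Week 24. Apply the same to TMA response.
3. Show this beside the protocol's Kaplan-Meier curve, which avoids a change of estimator late in an open-label study. If it replaces that curve, add an entry to SAP section 10.
4. If non-responders are instead held in the risk set, hold them to Day 183, not Day 169.
5. Limit the latest-detection date to the sustained analysis, so that the any-time analysis uses the first occurrence.

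The cost is SAP wording and one standard procedure. No new data are needed: dates of death (Protocol 6.5.7.3) and of study withdrawal (Protocol 6.3.3.2) are already collected. The competing-risk change leaves the curve equal or lower; the first-occurrence correction can move the any-time curve earlier.

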#### 6.5.7.3 Overall survival, time to response, duration of response, TA-TMA relapse

Overall survival will be assessed at Day 100 from the day of TA-TMA diagnosis and at Week 24 from treatment start. The day of TA-TMA diagnosis will be defined as the earliest date when all required laboratory criteria outlined in Inclusion Criterion #3 are met. Date of death and reason for death will be collected (whether related to TA-TMA or not).

Time to clinical/TMA response will be measured from the time of first IMP dose to the first documentation of attainment of a clinical or of a TMA response as defined in Section 5.2.1. Duration of clinical and of TMA response will be measured from the first documentation of attainment of a response until TA-TMA relapse.

Confidential Page 58 of 89

[figure not shown]
Pegcetacoplan/TA TMA

Clinical Study No: Sobi.PEGCET-201

TA-TMA relapse will be defined as reappearance of all laboratory markers as outlined in Inclusion Criterion #3 in a patient who has reached a clinical response.

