8.8.2.8 DURATION OF CLINICAL RESPONSE

Duration of clinical response (weeks) is defined as the time from the first observed clinical response until the response criteria is no longer fulfilled or until end of study. Duration of response will be defined for patients with clinical response without meeting an ICE. Mean and median duration of response, together with their 95% CI will be estimated using Kaplan-Meier method. Kaplan-Meier curves will also be presented. The start date will be defined as the date of the earliest clinical response. Loss of clinical response as per appendix I (Section 13.1) reported TA-TMA relapse (from Survival Status eCRF form), and death from any cause will be

Page 27 of 39

considered events, with the date of loss of clinical response, date of first reported TA-TMA relapse or date of death, whichever occurs first, defining the event date. Patients without events (i.e., still in clinical response) up to Week 24 will be censored at the date of the last clinical response evaluation prior to end of study.

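### SAP 8.8.2.6 does not limit its re-detection rule to the sustained-response analysis, so in the any-time analysis it conflicts with time to first response

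*SAP*

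**What the plan says.** Protocol 6.5.7.3 measures time to response from the first dose to the "first documentation of attainment of a clinical or of a TMA response". Protocol 8.3.4.2 defines it as the "time from study Day 1 to first occurrence of clinical response". Neither section has a rule for response that is lost and regained.

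SAP 8.8.2.6 opens the same way, running from "the date of first exposure to the study drug to the first occurrence of clinical response". It then sets up two analyses:

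- **Any-time analysis.** The patient is "considered as a responder even if not any longer in clinical response at week 24 or not (sustained response not required".
- **Sustained analysis.** The "response must be sustained until Week 24".

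Further down, the same section deals with response that is lost and then redetected: "the date of clinical response will be defined as the date when the most recent clinical response was detected". The sentence names neither analysis. The next one adds: "For sustained response, this date will be the event date if the patient is in clinical response at week 24".

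SAP 8.8.2.7 analyses time to TMA response in the same way. For duration of response, SAP 8.8.2.8 states: "The start date will be defined as the date of the earliest clinical response". SAP 8.8.2.9 does the same for TMA response. SAP section 10, which lists departures from the protocol, does not mention the re-detection rule.

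**The concern.** For a patient who loses and regains response, the first occurrence and the most recent detection are different dates, and SAP 8.8.2.6 prescribes both. In the any-time analysis, which is meant to show how soon patients first respond, a programmer following the text could use the later date. Three things would follow:

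- The result would no longer be the protocol's endpoint, and no departure would be recorded.
- A patient who regains response would look slower than an otherwise identical patient who loses it for good.
- Time to response and duration of response would start on different dates for the same patient, and the response could be scored as ending before it is scored as beginning.

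The pattern does not need a dramatic clinical course. Appendices I and II derive response from the values at a single visit, with no confirmation. One LDH value at or above 1.5 x ULN, one platelet count below the threshold, or one platelet transfusion in the preceding 7 days is enough to switch response off at that visit. Protocol Table 1 schedules the evaluation at every visit from Week 1.

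**Working it through.** **The plan's own figure.** The only stated design figure is a 72% probability of at least 8 responders among 12 at a true rate of 70% (SAP section 5). The exact binomial tail is P(X ≥ 8 | n = 12, p = 0.70) = 0.7237, so it reproduces. The point does not depend on it; it only supplies 8 of 12 as a natural number of responders for the illustration below.

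**Range of the delay.** The scheduled evaluation days in Protocol Table 1 are 8, 15, 22, 29, 43, 57, 71, 85, 99 (optional treatment only), 113, 141 and 169. With one loss and one regain, delay = day of re-detection − day of first response, on nominal visit days.

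- Shortest: response Day 8, loss Day 15, regain Day 22. Delay 22 − 8 = 14 days, or 2 weeks.
- Longest: response Day 8, any loss in between, regain Day 169. Delay 169 − 8 = 161 days, or 23 weeks.

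There are 165 possible orderings of response, loss and regain without the Day 99 visit, and 220 with it. The delay is at least 28 days in 97% and 98% of them, and at least 56 days in 82% and 84%. These count visit patterns and say nothing about how probable each is.

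**One patient worked through.** First response Day 29, loss Day 57, regain Day 85, with weeks = (study day − 1)/7:

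| Quantity | Calculation | Result |
|---|---|---|
| Time to response, first occurrence | (29 − 1)/7 | 4.0 weeks |
| Time to response, most recent detection | (85 − 1)/7 | 12.0 weeks |
| Duration under SAP 8.8.2.8 | (57 − 29)/7 | 4.0 weeks, ending Day 57 |

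Under the re-detection rule the response begins on Day 85, 28 days after its scored duration ended. The same patient without the regain is scored at 4.0 weeks.

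**The 100-day cap.** SAP 8.8.2.6 says time to response is analysed like overall survival at Day 100. SAP 8.8.2.4 censors at 100 days any date more than 100 days after the start. Day 85 is 84 days after first dose, so the example above is unaffected. Day 113 is 112 days after first dose and Day 141 is 140. If the cap is inherited literally, a response dated there becomes a censored observation at 100 days (100/7 = 14.3 weeks).

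**Effect on the median.** This uses assumed data, because the documents give no response times and no rate of loss and regain. Take 12 patients: 8 first respond at Weeks 2, 3, 4, 4, 6, 8, 10 and 12, and 4 do not respond and are followed throughout. The median is the earliest time at which the Kaplan-Meier cumulative proportion reaches 0.5. Early responders (first response Weeks 4, 4 and 6) are re-dated to Week 20.

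| Patients re-dated | Median, no cap | Median, cap inherited |
|---|---|---|
| 0 | 8 weeks | 8 weeks |
| 1 | 10 weeks | 10 weeks |
| 2 | 12 weeks | 12 weeks |
| 3 | 20 weeks | not reached (5/12 = 0.417 by Week 12, no later event) |

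**The case against.** The strongest reply is that the rule was only ever meant for the sustained analysis. The one sentence that turns the re-detected date into an event date begins with sustained response, and no sentence does so for the any-time analysis. On that reading the first occurrence still governs the any-time analysis, in agreement with the protocol and with the start date for duration. This is plausible and may well be the intent, but the text does not say it. Elsewhere in SAP 8.8.2.6, rules confined to the sustained analysis are introduced as such. The re-detection sentence is not, and it redefines the response date itself.

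Other parts of the reply stand:

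- In the sustained analysis, the start of the response still present at Week 24 is a coherent event date.
- The documents give no frequency of loss and regain. The median moves only if a first response at or before it is re-dated to after it.
- Loss of response under Appendix I is not TA-TMA relapse, which is defined separately through Inclusion Criterion #3. Nothing here says that relapsing patients in particular are affected.
- The endpoint is secondary and descriptive. Response is also summarised by visit and all data are listed, so the timing of first response stays visible.

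**Conclusion.** The point holds for the any-time analysis of both clinical and TMA response. The SAP contains two conflicting dating rules, and the literal scope of the second departs from the protocol without being recorded. For a patient with one loss and one regain, the error would be 2 to 23 weeks on nominal visit days, and the re-dated response would fall after that patient's scored duration had ended. With 12 patients one case could move the median; how far depends on response times that the documents do not give.

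A reader might infer more: that responders will be dated months late, that the sustained analysis is also wrong, or that the reported median is certain to be biased. The documents do not support this. The delay can be as short as two weeks, only patients who lose and regain response are affected, the sustained analysis is sound, and the narrower reading of the rule is possible. No error rate, sample size or primary endpoint is touched. The correction is still worth making, because two programmers could produce different results from the same text.

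**What to change.** In SAP 8.8.2.6, carried to 8.8.2.7 by reference:

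1. Confine the most-recent-detection sentence to the sustained-response analysis. It would help to label that endpoint as time to the start of the response sustained to Week 24, since first occurrence does not describe it.
2. State that in the any-time analysis the event date is the response date at the first visit meeting Appendix I (Appendix II for TMA response) without a preceding ICE, whatever happens later, and that this is also the start date for duration.
3. State that the 100-day censoring in SAP 8.8.2.4 does not apply to time to response in either analysis.

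The cost is two or three sentences and the matching programming specification. No new data are needed. The change should be settled before response patterns are tabulated, so that the event date is not chosen with the results in view.
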